12.1.3 Adverse device effect (ADE)

An adverse device effect (ADE) is an adverse event which is at least possibly related to the device. ADEs are not considered serious adverse events.

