12.1.2 Serious adverse event (SAE)

A serious adverse event (SAE) is any adverse event, occurring at any dose and regardless of causality that:

- Results in death
- Is life-threatening. Life-threatening means that the person was at immediate risk of death from the reaction as it occurred, i.e., it does not include a reaction which hypothetically might have caused death had it occurred in a more severe form.
- Requires or prolongs inpatient hospitalization (i.e., the event required at least a 24-hour hospitalization or prolonged a hospitalization beyond the expected length of stay). Hospitalization admissions and/or surgical operations scheduled to occur during the study period, but planned prior to study entry are not considered SAEs if the illness or disease existed before the person was enrolled in the trial, provided that it did not deteriorate in an unexpected manner during the trial (e.g., surgery performed earlier than planned).
- Results in persistent or significant disability/incapacity. Disability is defined as a substantial disruption of a person's ability to conduct normal life functions.
- Is a congenital anomaly or birth defect; or
- Is an important medical event when, based upon appropriate medical judgment, it may jeopardize the subject and require medical or surgical intervention to prevent one of the outcomes listed above. Examples of such medical events include allergic bronchospasm

LUMICELL CONFIDENTIAL

This document is confidential. Do not disclose or use except as authorized.

requiring intensive treatment in an emergency room or at home; blood dyscrasias or convulsions that do not result in inpatient hospitalization, or the development of drug dependency or drug abuse.

Events **not** considered to be serious adverse events are hospitalizations for:

- routine treatment or monitoring of the studied indication, not associated with any deterioration in condition, or for elective procedures
- elective or pre-planned treatment for a pre-existing condition that did not worsen
- respite care

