12.1.4 Unanticipated adverse device effects (UADEs)

Unanticipated adverse device effect (UADE) is any serious adverse effect on health or safety or any life-threatening problem or death cause by or associated with, a device, if that effect, problem, or death was not previously identified in nature, severity, or degree of incidence in the investigation plan or application, or any other unanticipated serious problem associated with a device that relates to the rights, safety or welfare of subjects.

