12.4 Reporting to Lumicell

12.4.1 Adverse Event Reporting

Non-serious adverse events should be captured in the Case Report Form and the Adverse Event Log.

All serious adverse events that occur after the initial dose of LUM015 Imaging Agent must be reported to Lumicell within 24 hours of becoming aware of the event. This includes events meeting the criteria outlined in the definitions section for SAEs. In addition to reporting the SAEs as outlined above, report to Lumicell adverse events that meet the following criteria within 24 hours of becoming aware of the event:

- Grade 2 (moderate) and Grade 3 (severe) Events – Only events that are unexpected and possibly, probably or definitely related/associated with the intervention

The principal investigator or delegated study team member must report each serious adverse event to Lumicell immediately after learning of the occurrence. In the event that the Investigator does not become aware of the serious adverse event immediately (e.g., subject sought treatment elsewhere), the principal investigator is to report the event immediately after learning of it and document the time of his or her first awareness of the adverse event. Report serious adverse events in writing to Lumicell according to the protocol training guidelines and:

To Lumicell:
[name].
[contact]
Email: [contact]

LUMICELL CONFIDENTIAL

This document is confidential. Do not disclose or use except as authorized.

[contact]

The Case Report Form (CRF) for a Serious Adverse Event should be completed as soon as possible after notifying Lumicell of the event. Written notification to Lumicell is required as indicated above in addition to the completion of the SAE CRF.

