12.4.3 Non-Serious Adverse Event and Adverse Device Effect Reporting

Non-serious adverse events and non-serious adverse device effects will be reported to Lumicell on the adverse events Case Report Forms.

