12.8 Monitoring of adverse events/adverse device effects and period of observation

All adverse events and adverse device effects, both serious and non-serious, and deaths that are encountered from initiation of study intervention and throughout the study, should be followed to

LUMICELL CONFIDENTIAL

This document is confidential. Do not disclose or use except as authorized.

their resolution, or until the principal investigator assesses them as stable, or the principal investigator determines the event to be irreversible, or the subject is lost to follow-up. The presence and resolution of AEs, ADEs, SAEs and UADEs (with dates) should be documented on the appropriate case report form and recorded in the subject's medical record to facilitate source data verification.

For some SAEs/UADEs, the investigator, Sponsor, or designee may follow-up by telephone, fax, and/or monitoring visit to obtain additional case details deemed necessary to appropriately evaluate the SAE/UADE report (e.g., hospital discharge summary, consultant report, or autopsy report).

Subjects should be instructed to report any serious post-study event(s) that might reasonably be related to participation in this study. The principal investigator should notify Lumicell and the IRB of any unanticipated death or adverse event occurring after a subject has discontinued or terminated study participation that may reasonably be related to the study.

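### Protocol 12.1.3 says adverse device effects are not SAEs, which contradicts 12.1.2 and 12.8 and, read literally, empties the device-related cells of the SAE tables

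*Protocol*

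**What the plan says.** Protocol 12.1.3 makes an ADE a kind of adverse event, namely one with at least a possible link to the device. It then adds, without qualification, "ADEs are not considered serious adverse events".

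The neighbouring sections say otherwise:

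- 12.1.2 defines an SAE as "any adverse event, occurring at any dose and regardless of causality" that meets one of the listed criteria. One criterion is inpatient hospitalization, explained as "the event required at least a 24-hour hospitalization or prolonged a hospitalization beyond the expected length of stay". The exceptions listed there concern certain hospitalizations and do not mention device effects.
- 12.8 requires follow-up of "All adverse events and adverse device effects, both serious and non-serious, and deaths".
- 12.1.4 defines an unanticipated adverse device effect (UADE) as, among other things, "any serious adverse effect on health or safety" that was not previously identified.
- 12.4.1 says that SAEs after dosing "must be reported to Lumicell within 24 hours of becoming aware of the event", and adds that this covers events that satisfy the SAE criteria in the definitions section. For the rest it says "Non-serious adverse events should be captured in the Case Report Form and the Adverse Event Log".
- 12.4.3 says "Non-serious adverse events and non-serious adverse device effects will be reported to Lumicell on the adverse events Case Report Forms".

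SAE status also drives the immediate notice to the DSMB chair (Protocol 13.4), the SAE summaries by severity and by relatedness to drug or device (Protocol 2.2 endpoint q and 15.4.4, SAP 3.3 endpoint u) and the SAE listing (SAP 4.8). Neither document says how a serious ADE is to be classified.

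**The concern.** A device-related event that meets a 12.1.2 criterion is an SAE under 12.1.2 and is not one under 12.1.3. Protocol 11.3 names infections and hematomas among the device events to be monitored. One that led to a hospital stay of 24 hours or more would meet 12.1.2 and still be excluded by 12.1.3.

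Two things are at stake. The first is the safety tables. If no ADE can be an SAE, no SAE can be possibly, probably or definitely related to the device, and a reported zero in those cells would reflect a definition and say nothing about device safety. The second is the expedited process, since the chair notice and the 24-hour report are tied to SAE status or SAE criteria. In addition, Protocol 12.1.6 gives the Medical Monitor the final word on relatedness. Under 12.1.3, SAE status would therefore turn on a causality decision, which 12.1.2 expressly rules out.

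**Working it through.** **Do the sections conflict?** An ADE is an adverse event (12.1.3). Any adverse event that meets a criterion is an SAE, whatever its cause (12.1.2). So an ADE that meets a criterion is an SAE, and 12.1.3 denies this. 12.8 speaks directly of serious ADEs. The conflict with these two sections is direct. Other places presuppose serious device effects:

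- 12.1.4 defines one class of them.
- 12.4.2 sends UADEs to the sponsor on the SAE form and SAE CRF.
- 12.4.3 needs the qualifier non-serious only if serious ADEs exist.
- 8.6 lists a death related to the imaging device as a potential stopping event.
- The SAE summaries by drug or device relatedness would need no device stratum otherwise.
- 9.3 counts the imaging device as investigational product, so the chair notice in 13.4 extends to device-attributable SAEs.

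**What happens to a serious, anticipated device effect?** Three readings are open.

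| Reading | SAE list, SAE summaries, chair notice | 24-hour report |
|---|---|---|
| A. 12.1.2 governs | Included | Required |
| B. 12.1.3 makes every ADE non-serious | Excluded | Lost; CRF and log only, with no time limit stated |
| C. 12.1.3 removes only the SAE label | Excluded | May still apply, because 12.4.1 also refers to events that meet the SAE criteria |

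The other expedited routes do not clearly catch it. The Grade 2 and 3 route in 12.4.1 requires an unexpected event, and 12.4.2 requires an unanticipated one.

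**How many events?** The plan gives no figure to reproduce. Inputs:

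- Protocol 11.3 reports no adverse device events to date.
- Protocol 11 gives 15 + 45 + 234 = 294 enrolled in the three feasibility phases, 289 of them injected.
- Protocol 15.3.1 uses 230 Phase C patients for the residual-cancer proportion.
- SAP 1.1 gives 406 enrolled in this study.

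For 0 events in n patients, the exact one-sided 95% upper limit is 1 − 0.05^(1/n).

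- n = 294: 0.01014; × 406 = 4.12
- n = 289: 0.01031; × 406 = 4.19
- n = 230: 0.01294; × 406 = 5.25

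These are upper limits for ADEs of any seriousness; the point estimate is 0. The documents give no serious fraction. With assumed fractions of 10%, 25% and 50%, the n = 294 limit becomes 0.41, 1.03 and 2.06 serious ADEs. Those fractions only illustrate a range and have no source in the documents.

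**The case against.** The best defence is that one stray sentence is out of line with a protocol that otherwise treats device effects as capable of being serious, and that most sites would follow 12.1.2. The balance of the text does favour that reading. It does not cure the sentence, because nothing says which clause governs. It might be read to mean that ADEs are not automatically SAEs, but it does not say so. It might be meant to leave serious effects to the UADE category, but that conflicts with 12.8 and leaves serious, previously identified effects without a category.

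Three other objections stand and limit the point.

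- A reader might infer that any reading giving effect to 12.1.3 loses the 24-hour report. The documents do not support that. The sentence in 12.4.1 that refers to the SAE criteria does not depend on the label, so only reading B clearly loses the report.
- A reader might also infer that the 24-hour limit in 12.4.1 conflicts with the 10-working-day limit in 12.4.2 for a UADE that meets 12.1.2. It does not: the second is an outer limit, and a report within 24 hours satisfies both.
- The affected class may be nearly empty. A serious infection or hematoma that differs in nature, intensity or frequency from what is listed is unexpected (12.1.5.2), or may be a UADE (12.1.4), and other rules then apply. What is listed as anticipated is in the Investigator's Brochure, which is not among these documents.

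Nor would an affected event disappear. It is recorded on the CRF (12.2), reported to the IRB under its policy (12.5), reviewed by the Medical Monitor (13.2), included in the adverse event reports the DSMB receives (13.4) and tabulated by severity. Severity is CTCAE grade (12.1.1), however, and grade does not show that an event was serious.

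**Conclusion.** The sentence in 12.1.3 is wrong as written: an internal contradiction, not a matter of preference. Taken literally, it removes a serious, anticipated device effect from the SAE list and summaries and from the chair notice; whether the 24-hour report is also lost depends on the reading.

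Severity is low. The expected number of affected events is small and may be zero: at most about 4 to 5 ADEs of any seriousness in 406 patients at the 95% upper limit, with serious, anticipated ones a subset of unknown size. That count assumes that the patients in the denominator were imaged in the cavity and that the feasibility rate carries over. Alpha, power and the co-primary endpoints are not affected. The textual conflict is certain; the practical consequence is less so, because it depends on the unseen list of anticipated effects and on how sites were trained.

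**What to change.** Delete or correct the sentence in Protocol 12.1.3 so that it agrees with 12.1.2 and 12.8: the seriousness of an ADE is judged by the 12.1.2 criteria irrespective of relatedness. State that a serious ADE counts as an SAE for 12.4.1, for the chair notice in 13.4, and for the SAE outputs in Protocol 2.2 (endpoint q), Protocol 15.4.4, SAP 3.3 (endpoint u) and SAP 4.8. Before those tables are produced, check every recorded ADE against the 12.1.2 criteria.

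The cost is a one-sentence correction or a clarification memo, a short listing review of what is probably a handful of events, and possibly a few late expedited reports. Since the SAP already speaks of 406 patients enrolled, much of the benefit for prospective reporting has probably passed. The listing review is what still protects the SAE tables.

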12.1.4 Unanticipated adverse device effects (UADEs)

Unanticipated adverse device effect (UADE) is any serious adverse effect on health or safety or any life-threatening problem or death cause by or associated with, a device, if that effect, problem, or death was not previously identified in nature, severity, or degree of incidence in the investigation plan or application, or any other unanticipated serious problem associated with a device that relates to the rights, safety or welfare of subjects.

12.1.5 Expectedness

Adverse events (AEs) and adverse device effects (ADEs) can be 'Expected' or 'Unexpected'.

12.1.5.1 Expected adverse event or adverse device effect

Expected AEs and ADEs are those that have been previously identified as resulting from administration of the agent or use of the device. For the purposes of this study, an AE or ADE is considered expected when it appears in the current AE/ADE list, the Investigator's Brochure, the Instructions For Use or is included in the informed consent document as a potential risk.

12.1.5.2 Unexpected adverse event or adverse device effect

For the purposes of this study, an AE or ADE is considered unexpected when it varies in nature, intensity or frequency from information provided in the current AE/ADE list, the Investigator's Brochure, the Instructions For Use, or when it is not included in the informed consent document as a potential risk.

12.1.6 Attribution

Attribution is the relationship between an adverse event or serious adverse event and the study treatment. Attribution will be assigned as follows:

- Definite – The AE or ADE is clearly related to the study treatment.
- Probable – The AE or ADE is likely related to the study treatment.
- Possible – The AE or ADE may be related to the study treatment.
- Unlikely - The AE or ADE is doubtfully related to the study treatment.
- Unrelated - The AE or ADE is clearly NOT related to the study treatment.

Final determination of relatedness will be made by the Medical Monitor, who will integrate all data, including investigator's assessment of relatedness.

12.2 Procedures for recording and reporting safety

The principal investigator will assess the occurrence of AEs, SAEs, ADEs and UADEs at all subject evaluation time points during the study.

All AEs, SAEs, ADEs and UADEs whether reported by the subject, discovered during questioning, directly observed, or detected by physical examination, laboratory test or other means, will be recorded in the subject's medical record and on the appropriate study-specific case report forms.

For events related to the imaging agent, the descriptions and grading scales found in the revised NCI Common Terminology Criteria for Adverse Events (CTCAE) version 5.0 will be utilized for AE reporting. All appropriate treatment areas should have access to a copy of the CTCAE version 5.0.

A copy of the CTCAE version 5.0 can be downloaded from the CTEP website at:

http://ctep.cancer.gov/protocolDevelopment/electronic_applications/ctc.htm.

12.3 Reporting requirements

The study must be conducted in compliance with FDA regulations, local safety reporting requirements, and reporting requirements of the principal investigator and/or IRB.

The Investigator will be responsible to report SAEs that occur at the Institution to the IRB in accordance with IRB requirements. It is the responsibility of the principal investigator to report serious adverse events to Lumicell and/or others as described below.

12.4 Reporting to Lumicell

12.4.1 Adverse Event Reporting

Non-serious adverse events should be captured in the Case Report Form and the Adverse Event Log.

All serious adverse events that occur after the initial dose of LUM015 Imaging Agent must be reported to Lumicell within 24 hours of becoming aware of the event. This includes events meeting the criteria outlined in the definitions section for SAEs. In addition to reporting the SAEs as outlined above, report to Lumicell adverse events that meet the following criteria within 24 hours of becoming aware of the event:

- Grade 2 (moderate) and Grade 3 (severe) Events – Only events that are unexpected and possibly, probably or definitely related/associated with the intervention

The principal investigator or delegated study team member must report each serious adverse event to Lumicell immediately after learning of the occurrence. In the event that the Investigator does not become aware of the serious adverse event immediately (e.g., subject sought treatment elsewhere), the principal investigator is to report the event immediately after learning of it and document the time of his or her first awareness of the adverse event. Report serious adverse events in writing to Lumicell according to the protocol training guidelines and:

To Lumicell:
[name].
[contact]
Email: [contact]

LUMICELL CONFIDENTIAL

This document is confidential. Do not disclose or use except as authorized.

[contact]

The Case Report Form (CRF) for a Serious Adverse Event should be completed as soon as possible after notifying Lumicell of the event. Written notification to Lumicell is required as indicated above in addition to the completion of the SAE CRF.

12.4.2 Unanticipated Adverse Device Effects

All unanticipated adverse device effects (UADEs) that occur during the study must be reported to Lumicell using the provided SAE form.

The principal investigator must report each unanticipated adverse device effect to Lumicell as soon as possible, but in no event later than 10 working days after the Investigator learning of the occurrence. Investigators should document their initial knowledge of the event. Report unanticipated adverse device in writing to Lumicell according to protocol training guidelines and:

To Lumicell:
[name].
[contact]
Email: [contact]
[contact]

The Case Report Form (CRF) for a UADE should be completed as soon as possible after notifying Lumicell of the event. Written notification to Lumicell is required as indicated above in addition to the completion of the SAE CRF.

Lumicell will immediately conduct an evaluation of a UADE and must report the results of the evaluation to FDA, all reviewing IRBs, and participating investigators within 10 working days after the sponsor first receives notice of the effect. This evaluation will determine any action needed as described in section 8.6 of this protocol.

12.4.3 Non-Serious Adverse Event and Adverse Device Effect Reporting

Non-serious adverse events and non-serious adverse device effects will be reported to Lumicell on the adverse events Case Report Forms.

12.5 Reporting to the Institutional Review Board (IRB)

The investigative site will report adverse events, serious adverse events, adverse device effects and unexpected adverse device effects directly to the IRB in accordance with the institution's or Central IRB policy.

12.6 Reporting to the Food and Drug Administration (FDA)

Lumicell or its agents will report to the FDA via their IDE as required in 21 CFR Parts 312 & 812 and as additionally described in this protocol.

12.7 Reporting to Hospital Risk Management

The principal investigator will report to their local Risk Management office any subject safety reports or sentinel events that require reporting according to institutional policy.

12.8 Monitoring of adverse events/adverse device effects and period of observation

All adverse events and adverse device effects, both serious and non-serious, and deaths that are encountered from initiation of study intervention and throughout the study, should be followed to

LUMICELL CONFIDENTIAL

This document is confidential. Do not disclose or use except as authorized.

their resolution, or until the principal investigator assesses them as stable, or the principal investigator determines the event to be irreversible, or the subject is lost to follow-up. The presence and resolution of AEs, ADEs, SAEs and UADEs (with dates) should be documented on the appropriate case report form and recorded in the subject's medical record to facilitate source data verification.

For some SAEs/UADEs, the investigator, Sponsor, or designee may follow-up by telephone, fax, and/or monitoring visit to obtain additional case details deemed necessary to appropriately evaluate the SAE/UADE report (e.g., hospital discharge summary, consultant report, or autopsy report).

Subjects should be instructed to report any serious post-study event(s) that might reasonably be related to participation in this study. The principal investigator should notify Lumicell and the IRB of any unanticipated death or adverse event occurring after a subject has discontinued or terminated study participation that may reasonably be related to the study.

12.9 Protocol deviations

Protocol deviations to ongoing studies are any unapproved changes in the study design and/or procedures that are within the Investigator's control and not in accordance with the IRB approved protocol. The Principal Investigator or designee will enter all protocol deviations on the Protocol Deviation Tracking Log provided by Lumicell. The log will be reviewed and updated as necessary by the site team. The site monitor (CRA) will review the log during their interim monitoring visit and obtain a copy of the log for Lumicell files. Additionally, the site should inform the IRB of record of the protocol deviation following the IRB's policy on reporting deviations.

